| TEST PRODUCT, DOSE, AND ROUTE OF ADMINISTRATION | 
Synvisc G-F 20 will be injected in the symptomatic knee using a standard supine lateral approach using a 20-gauge needle. Patients will be treated at baseline and followed out to three years. Patients may return for retreatment as early as 4 months post their prior injection if they meet the retreatment criteria pain levels for Worst Knee Pain. If the subjects need another injection, the follow-up cycle will restart at Visit 1 and the subject will be seen every 6 months and followed-up for 3 years.
 |
| CONTROL PRODUCT, DOSE AND ROUTE OF ADMINISTRATION | N/A |

| | |
|---|--|
| 
DURATION OF SUBJECT PARTICIPATION AND DURATION OF STUDY
 | 
Patients may return for retreatment as early as 4 months post their prior injection if they meet the retreatment criteria pain levels for Worst Knee Pain. If the subjects need another injection, the follow-up cycle will restart at Visit 1 and the subject will be seen every 6 months and followed-up for 3 years.
 
Approximate Time Requirements:
 
 • Baseline Screening: Informed Consent, Physical exam, patient questionnaire, injection, X-ray, walk test (Approx. 2 hours) and accelerometer test (3 days) • 6 months after injection: Physical exam, patient questionnaire, walk test (Approx. 1 hr) and accelerometer test (3 days) • 12 months after injection: Physical exam, patient questionnaire, walk test (Approx. 1 hr) and accelerometer test (3 days) • 18 months after injection: Physical exam, patient questionnaire, walk test (Approx. 1 hr) and accelerometer test (3 days) • 24 months after injection: Physical exam, patient questionnaire, walk test (Approx. 1 hr) and accelerometer test (3 days) • 30 months after injection: Physical exam, patient questionnaire, walk test (Approx. 1 hr) and accelerometer test (3 days) • 36 months after injection: Physical exam, patient questionnaire, walk test (Approx. 1 hr) and accelerometer test (3 days) • 15 min email or phone contact at 6, 12, and 18 weeks post each injection and clinic visit (total 4.5 hrs) 
Total time for the study will be approximately 8 clinical hours over 3 years, 21 days for the accelerometer test and 4.5 hrs of email/phone contact.
 |

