duration of the study. Patients can receive any other conservative treatments (e.g., oral medications, physical or other therapy, acupuncture, etc., except other injection treatments) and current treatments will be documented during each patient encounter. An initial injection of hylan G-F 20 will be injected in the symptomatic knee using a standard supine lateral approach using a 20 gauge needle. A face to face follow up visit will be carried out 6 months after first injection with additional face to face meetings every 6 months thereafter unless the subject requires an additional injection of hylan G-F 20. Hylan G-F 20 treatments can be administered up to three times each year during the study duration. After each injection, follow up measures will be carried out using secure e-mail or phone contact at 6 weeks, 12 weeks, 18 weeks after each in-office evaluation or injection. Follow up will consist of WOMAC, Lysholm score, and Tegner score. . Patients may return for retreatment of hylan G-F 20 if symptoms recur after at least 4 months following their previous injection and they meet the inclusion criteria for pain levels on the following WOMAC questions A1 (How much pain have you had walking on a flat surface?), C8 (How much difficulty have you had going down the stairs?), C9 (How much difficulty have you had when going up the stairs?), C10 (How much difficulty have you had when getting up from a sitting position?) and/or C23 (How much difficulty have you had while doing heavy household chores?). Inclusion criteria for pain level is defined by selecting moderate, severe, or extreme on all questions A1, C8, C9, C10 and/or C23. Those subjects who select mild or no pain levels on any of A1, C8, C9, C10 and/or C23, will not meet the criteria for WOMAC pain level and retreatment. Patients requiring three injections of hylan G-F 20 in 4 months or less will be allowed to exit the cohort after their six-month follow up following the third injection. Otherwise, patients will be followed until they reach the 3 year follow up, or drop out for other injection treatments or surgical treatment. Therefore, patients would potentially be able to receive up to 9 injections during the 3 year study.

Total time for the study will be approximately 8 clinical hours over 3 years, 21 days for the accelerometer test and 4.5 hrs of email/phone contact.

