4 CRITERIA FOR EVALUATION

4.1 Primary Efficacy Endpoint

Co-Primary endpoints

- o Proportion of subjects reporting being in PASS during at least one Study Contact Point during entire 36 month study period
- o Proportion of Study Contact Points that each subject reports being in PASS during entire 36 month study period

Secondary endpoints

- o Change in scores over 36 months for:

- o Worst Knee Pain
- o Five KOOS domains
- o SF-12
- o 12-minute walk test
- o 3-day accelerometer test

The primary endpoint for the study will be analyzed using a responder analysis. The proportion of responders following injection within the 6 months following the baseline injection will be calculated based on Worst Knee Pain scores. A specific timeframe of interest will be the initial 6 months of treatment following the second and any subsequent hylan G-F 20 injection.

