13 STATISTICAL METHODS AND CONSIDERATIONS

Prior to the analysis of the final study data, a detailed Statistical Analysis Plan (SAP) will be written describing all analyses that will be performed. The SAP will contain any modifications to the analysis plan described below.

Data Sets Analyzed

The primary endpoint is based on a responder analysis. Response is defined as maintaining a Worst Knee Pain score ≤ 3 on a 0-10 pain scale throughout the 6 months following the baseline injection. Trial success will be based on a non-inferiority test (with 20% non-inferiority threshold) of this response rate in comparison to an external criterion of 70% (Bellamy 2010). Secondary endpoints include determining the duration of response after subsequent injection, determining the effects of treatment on activity levels and quality of life, and describing the three-year time course of each of the study endpoints. The sample size will be $n=150$ subjects followed for up to 3 years after baseline injection. The power to conclude non-inferiority for a true response rate of 65% is better than 92%.

Demographic and Baseline Characteristics

The following demographic variables at screening will be summarized by: race, gender, age, height and weight.

Analysis of Primary Endpoint

The primary endpoint for the study will be analyzed using a responder analysis. The proportion of responders following injection within the 6 months following the baseline injection will be calculated based on Worst Knee Pain scores ≤ 3 on a 0-10 pain scale, which is a threshold consistent with other similar studies (Tubach 2005, Bellamy 2010). The primary endpoint is defined as non-inferiority (with 20% non-inferiority threshold) of the proportion of responders in our study relative to an external criterion of 70% for the responder proportion (Bellamy 2010).

Primary Statistical Analysis: Define the true probability of a subject being a responder as π and the non-inferiority threshold $\delta_{NI} = 0.20$. We require the test of

$$H_0: \pi < 0.70 - \delta_{NI} = 0.50$$

vs. the alternative

$$H_1: \pi \geq 0.70 - \delta_{NI} = 0.50.$$

Non-inferiority will be accepted if the null hypothesis can be rejected with a 2.5% one-sided type I error. To test this hypothesis, we will use the Wilson-Agresti method for a single binomial proportion. Non inferiority will be accepted if the 95% Wilson-Agresti (REF BROWN ET AL 2001) interval for the proportion of responders excludes the null rate of 0.50.

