Missing Data:For the analysis of the percentages of positive responders, patients who discontinue the study prior to the Week 26 assessment due to either target knee-related AEs or due to lack of efficacy will be classified as non-responders in the efficacy analysis. Patients who discontinue the study for other reasons will have the responder status imputed using the last observation carried forward (LOCF) method.

Operating Characteristics

The following table shows the power to accept non-inferiority for two assumptions on sample size (n=150 and a smaller sample size reflecting potential dropout of n=120):

| True Responder Rate (□. | Sample Size n=150 | Sample Size n=120 |
|----------------------------|----------------------|----------------------|
| 0.60 | 72% | 61% |
| 0.65 | 97% | 92% |
| 0.70 | >99% | >99% |
| 0.75 | >99% | >99% |

Table 1. Power to conclude non-inferiority for variety of true responder rates and two values for sample size.

Thus, even after conservatively accounting for subject dropout, we will be well-powered to conclude non-inferiority if the true responder rate is at least 65%.

Secondary Outcomes:

- **Duration of response to subsequent injections:** Though symptoms can be improved for periods up to 6 months, pain symptoms can recur in which case patients will receive a subsequent injection. The duration of these repeated treatments of hylan G-F 20 will be studied.

- **Effect of treatment on activity levels and quality of life:** The effects of treatment with hylan G-F 20 on activity levels (using objective activity measures utilizing accelerometer

and Physical Activity Enjoyment Scale) and quality of life scores (WOMAC, SF-12) comparing baseline to treatment at 3 months.

- **Three year follow up:** Patients will be followed for up to three years. We will examine the time courses of pain score, activity level, and quality of life over the entire three year span.

Analysis of Secondary Endpoints

Secondary Analyses: Secondary endpoints will be analyzed using confidence intervals as no specific hypothesis tests are being conducted.

The following secondary analyses will be conducted:

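### Re-injection is allowed inside the 26-week primary window and no rule scores it, so a first-injection failure that leaves no disqualifying pain rating can be counted as a response to the baseline injection.

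*Combined protocol and SAP*

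**What the plan says.** - **Timing of retreatment.** Section 3.1 states: "Patients may return for retreatment of hylan G-F 20 if symptoms recur after at least 4 months following their previous injection". The synopsis (test product) agrees on timing: "Patients may return for retreatment as early as 4 months post their prior injection".
- **Trigger for retreatment.** Section 3.1, repeated in section 7.4.1 and the synopsis study design, uses WOMAC items: "Inclusion criteria for pain level is defined by selecting moderate, severe, or extreme on all questions A1, C8, C9, C10 and/or C23". The synopsis test-product entry instead allows it "if they meet the retreatment criteria pain levels for Worst Knee Pain" and gives no threshold.
- **After retreatment.** The synopsis says "the follow-up cycle will restart at Visit 1". Appendix 1 schedules no Worst Knee Pain rating at Visit 1. Section 9 schedules one at the contacts 6, 12 and 18 weeks after each injection or clinic visit.
- **Primary response.** Under Data Sets Analyzed, section 13 requires Worst Knee Pain to stay at 3 or less "throughout the 6 months following the baseline injection". Under Analysis of Primary Endpoint it speaks of scores of 3 or less within those 6 months, without saying whether one, all or the last must qualify.
- **Non-response.** Section 13 (Missing Data) classes as non-responders "patients who discontinue the study prior to the Week 26 assessment due to either target knee-related AEs or due to lack of efficacy". Those who discontinue for other reasons get last observation carried forward.
- **Later injections.** Section 4.1 adds: "A specific timeframe of interest will be the initial 6 months of treatment following the second and any subsequent hylan G-F 20 injection".

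Nothing in the document says how a re-injection before Week 26 is scored, or excludes ratings taken after it from the baseline injection's result.

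**The concern.** Aim 1 asks whether a 6 mL injection lowers pain over 26 weeks. A subject who needs a second injection within that time has not had 26 weeks of relief from the first. Such a subject has not discontinued, so neither the non-responder rule nor the carry-forward rule applies, and ratings after the second injection can enter the primary window.

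The error can only raise the responder proportion. That proportion is tested against a fixed 0.50 with no control arm, so nothing offsets the bias. The Kaplan-Meier analysis of duration of response to the initial injection has the same gap, because re-injection is not defined as an event.

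**Working it through.** **1. Timing.** Four months is 4 × 365.25/12/7 = 17.4 weeks; six months is 26.1 weeks. After the earliest re-injection, the restarted 6-week contact falls at 17.4 + 6 = week 23.4. That contact lies inside the window for any re-injection up to 26.1 − 6 = week 20.1. After a later re-injection, no restarted contact falls in the window. Whether the baseline cycle's 6-month visit still takes place is not stated, so those subjects are unclassified.

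**2. Route under the *throughout* definition.** A recorded score above 3 at weeks 6, 12 or 18 already makes the subject a non-responder. The gap needs a failure that is not recorded on this scale. Example: scores of 3 or less at weeks 6, 12 and 18; recurrence at week 19; retreatment at week 20 on WOMAC items, with no Worst Knee Pain rating at Visit 1; a score of 3 or less at the restarted contact at week 26. Every recorded value in the window then qualifies.

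**3. Route under an any-time reading of *within*.** The subject in step 2 was already a responder before re-injection, so re-injection changes nothing. The gap affects a different subject: above 3 at every contact before re-injection, and at 3 or less afterwards but before Week 26.

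**4. Reproducing the plan's power.** The decision rule is the smallest count x whose 95% Wilson lower limit exceeds 0.50. Power is the exact binomial tail P(X ≥ x | n, p).
- n=120: x = 71. Power is 61% at p = 0.60 and 92% at 0.65, as in section 13, Table 1.
- n=150: x = 88. Power is 66% at 0.60 and 96% at 0.65. Table 1's 72% and 97% correspond to x = 87, whose lower limit is 0.49998 and so does not strictly exclude 0.50. That is a separate matter; 88 is used below.

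**5. Effect on false success.** Let f be the share of *all* subjects who are true non-responders to the baseline injection but are counted as responders because of re-injection. The documents give no value for f, so it is assumed. With a true rate of 0.50, the chance of success is P(X ≥ x | n, 0.50 + f):

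| f | n=150 | n=120 |
|---|---|---|
| 0 | 2.0% | 2.7% |
| 3% | 9.5% | 10% |
| 5% | 21% | 20% |

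At n=150, 3% is 4.5 subjects and 5% is 7.5.

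**6. Effect of the correction on power.** If the planned 65% already includes such subjects, scoring them as non-responders gives P(X ≥ x | n, 0.65 − f). At f = 5% the rate is 0.60: power falls from 92% to 61% at n=120, and from 96% to 66% at n=150.

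**7. Later injections.** With re-injection every 4 months, consecutive 6-month windows overlap by 6 − 4 = 2 months. No rule says which injection those ratings belong to.

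**The case against.** The strongest reply is that the plan already catches most of these subjects. Under *throughout*, any recorded score above 3 means non-response. If retreatment depends on Worst Knee Pain, as the synopsis test-product entry says, a rating would be taken before re-injection and might itself exceed 3. Both points narrow the concern. Neither closes it: that entry gives no threshold, Appendix 1 schedules no such rating at Visit 1, and three other places use WOMAC items.

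A reader might infer more than the documents support:
- *That any subject whose first injection failed can count as a responder.* This depends on the definition. Steps 2 and 3 of the working describe different subjects, and neither route covers all failures.
- *That f is the re-injection rate, or that it could readily be large.* It is narrower: re-injected early, not otherwise a non-responder or responder under the definition in use, and scoring 3 or less afterwards. Nothing in the documents supports a particular value.
- *That a first-versus-repeat comparison is compromised.* None is planned. Aim 2 says that repeated treatment will be studied, and section 13 plans estimates with confidence intervals. Only the attribution of overlapping ratings is at issue.
- *That the plan assigns the restarted 6-week rating to the baseline injection.* It does not assign it at all.

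It can also be said that the synopsis rationale accepts repeat treatment as a way of keeping patients in an acceptable symptom state, and that section 4.1 lists 36-month co-primary endpoints that span retreatment. A strategy that includes retreatment is a legitimate question, but it is not Aim 1.

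Finally, section 13 promises a later, detailed SAP. That SAP could supply the rule. In an open-label, single-arm study, however, it might then be chosen by people who can see who was re-injected.

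**Conclusion.** The concern holds in this limited form. Retreatment is permitted inside the primary window, the non-response rule does not cover it, and the plan as written allows relief from a second injection to count towards the first. The direction, towards declaring non-inferiority, follows from the documents.

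The size does not. The percentages in the working rest on an assumed share of misclassified subjects and a true rate of exactly 0.50. They show that a handful of subjects would be enough to matter; they do not predict what will happen. Two inconsistencies determine how wide the gap is: the two responder definitions in section 13 and the two retreatment criteria.

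**What to change.** In section 13:
1. Use one responder definition, the *throughout* sentence, and align the other statements of the primary endpoint with it.
2. Class a subject who receives a further target-knee injection before the Week 26 assessment as a non-responder to the baseline injection, whatever later ratings show.
3. Use only ratings taken before re-injection for the first injection.
4. In the Kaplan-Meier analysis, count re-injection as loss of response and end each injection's window at the next injection.
5. Report the number re-injected before Week 26.

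The two statements of the retreatment criterion (Worst Knee Pain in the synopsis test-product entry; WOMAC items in sections 3.1 and 7.4.1 and the synopsis study design) must be reconciled. This review takes no position on which is right, and the analysis changes leave retreatment itself untouched.

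The change is to analysis wording, using injection dates that the accountability records in section 7.6 should supply. The cost is a lower reported response rate. If the planned 65% included such subjects, power is also below Table 1, for example 61% instead of 92% at n=120 if they are 5% of subjects. Section 13.6 describes the 70% reference as response at any time, and the documents do not show how re-injection was scored there, so the planning rate should be reconsidered under the chosen definition.

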 2. KOOS
 3. SF-12
 4. WOMAC

Email or phone contact at 6, 12 and 18 weeks post each injection and clinic visit to check for any changes in medical condition.

- Worst Knee Pain (0-10 NRS)
- Other treatment history
- Adverse events

| Office Visit | What you do |
|--|---|
| 1-3 weeks before starting study treatment | Physical exam X-ray Study questionnaire 12 minute walk test 3-day accelerometer test |
| Visit 1 - Baseline | Synvisc-One injection in the affected knee |

| | |
|--|---|
| 
Visit 2 – 6 months after injection Visit 3 – 1 year after injection Visit 4 – 1.5 years after injection Visit 5 – 2 years after injection Visit 6 – 2.5 years after injection
 
Email or phone contact at 6, 12 and 18 weeks after each injection and office visit
 | 
Physical exam Study questionnaire 12 minute walk test 3-day accelerometer test
 
Check up on your medical condition
 |
|--|---|

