11 DISCONTINUATION AND REPLACEMENT OF SUBJECTS

11.1 Early Discontinuation of Study Drug

A subject may be discontinued from study treatment at any time if the subject, the investigator, or the Sponsor feels that it is not in the subject's best interest to continue. The following is a list of possible reasons for study treatment discontinuation:

- Subject withdrawal of consent (or assent)
- Subject is not compliant with study procedures
- Adverse event that in the opinion of the investigator would be in the best interest of the subject to discontinue study treatment

- Protocol violation requiring discontinuation of study treatment
- Lost to follow-up
- Sponsor request for early termination of study
- Positive pregnancy test (females)

If a subject is withdrawn from treatment due to an adverse event, the subject will be followed and treated by the Investigator until the abnormal parameter or symptom has resolved or stabilized.

All subjects who discontinue study treatment should come in for an early discontinuation visit as soon as possible and then should be encouraged to complete all remaining scheduled visits and procedures.

All subjects are free to withdraw from participation at any time, for any reason, specified or unspecified, and without prejudice.

Reasonable attempts will be made by the investigator to provide a reason for subject withdrawals. The reason for the subject's withdrawal from the study will be specified in the subject's source documents.

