11.3 Replacement of Subjects

Subjects who withdraw from the study treatment in the first 6 months of the study will be replaced. Replacement injected will be requested from Genzyme based on need.

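### Two n=150 power entries do not follow the stated interval rule, and LOCF can credit a maintained response that was only partly observed

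*Combined protocol and SAP*

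**What the plan says.** All of the following is in the combined protocol and SAP.

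- **Endpoint.** Section 13, Data Sets Analyzed, defines response as keeping Worst Knee Pain at 3 or below "throughout the 6 months following the baseline injection". Analysis of Primary Endpoint, in the same section, speaks of the proportion of responders "within the 6 months following the baseline injection will be calculated based on Worst Knee Pain scores". The synopsis and section 4.1 also use the *within* wording.
- **Test.** The null rate is 0.70 − 0.20 = 0.50, at 2.5% one-sided. Success requires the 95% Wilson-Agresti interval to exclude 0.50.
- **Missing data.** Exits before Week 26 "due to either target knee-related AEs or due to lack of efficacy will be classified as non-responders in the efficacy analysis". For the rest, "Patients who discontinue the study for other reasons will have the responder status imputed using the last observation carried forward (LOCF) method".
- **Power table.** At true rates of 0.60 and 0.65 it gives 72% and 97% for n=150, and 61% and 92% for n=120. It concludes that "even after conservatively accounting for subject dropout, we will be well-powered to conclude non-inferiority if the true responder rate is at least 65" per cent.
- **Score collection.** Section 9 lists Worst Knee Pain under "Email or phone contact at 6, 12 and 18 weeks post each injection and clinic visit". The synopsis (Study Design) and sections 3.1 and 7.4.1 say these contacts consist of WOMAC, Lysholm and Tegner. Appendix 1 schedules Worst Knee Pain only at screening and the 6-monthly visits.
- **Replacement.** Section 11.3: "Subjects who withdraw from the study treatment in the first 6 months of the study will be replaced". Section 11.1 asks subjects who stop treatment to attend a discontinuation visit and says they "then should be encouraged to complete all remaining scheduled visits and procedures". Data Sets Analyzed names no analysis population.

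**The concern.** Trial success rests on one single-arm test against a fixed rate. No control arm shares an error in how early exits are scored, so the scoring rule acts directly on the result. With a pass mark of 88/150, a trial that counts 90 responders fails once 3 of them are removed (90 − 3 = 87).

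Three things do not fit together:

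- The printed n=150 power does not come from the stated rule.
- A response that must be maintained cannot be confirmed from a partial record, yet LOCF may assign it.
- The missing-data rule gives every early exit a status and so keeps it in the denominator, whereas the n=120 column removes exits altogether.

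The detailed SAP is due only before the final analysis of an open-label study, so outcomes could be visible before these rules are fixed.

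**Working it through.** **1. Cutoff and power table.** Inputs from section 13: null 0.50, 95% interval, n=150 or 120. The Wilson lower limit exceeds 0.50 exactly when (x − n/2)/√(n/4) > 1.95996.

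- n=120: 71 gives 11/√30 = 2.008 (pass); 70 gives 10/√30 = 1.826 (fail). Cutoff 71.
- n=150: 88 gives 13/√37.5 = 2.123 (pass); 87 gives 12/√37.5 = 1.9596 (fail). Cutoff 88.

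At 87/150 the lower limit is 0.49998 (Wilson) or 0.49996 (Agresti-Coull), so either reading of the method's name gives 88. Exact power is P(Bin(n, p) ≥ cutoff):

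| n, cutoff | Error at 0.50 | Power at 0.60 | Power at 0.65 | Printed |
|---|---|---|---|---|
| 120, 71 | 2.7% | 61.2% | 92.3% | 61% / 92% |
| 150, 88 | 2.0% | 66.3% | 95.5% | 72% / 97% |
| 150, 87 | 3.0% | 72.1% | 96.9% | 72% / 97% |

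The n=120 column reproduces. The two n=150 entries match only the cutoff of 87.

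**2. LOCF under the *throughout* wording.** The documents give no exit rates by week, so everything here is assumed. There are four assessments (weeks 6, 12, 18 and 26). The chance of a score of 3 or below at week 6 is a, and the chance of staying there from one assessment to the next is r. Setting a·r³ = 0.50 puts the true maintained rate at the null. A share d of subjects leave, all for reasons that attract LOCF and unrelated to pain.

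- Exits spread evenly after weeks 6, 12 and 18: credited rate q = a(1 + r + r²)/3.
- A quarter of exits before week 6: these carry forward the baseline score, which section 5.2 requires to be 4 to 8, so they are non-responders and q = a(1 + r + r²)/4.

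Error = P(Bin(150, 0.50(1 − d) + d·q) ≥ 88):

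| r | q, all after week 6 | Error, d = 10% / 20% | q, quarter before week 6 | Error, d = 10% / 20% |
|---|---|---|---|---|
| 0.95 | 0.555 | 2.8% / 3.8% | 0.416 | 1.2% / 0.7% |
| 0.90 | 0.620 | 4.0% / 7.2% | 0.465 | 1.65% / 1.3% |
| 0.85 | 0.698 | 5.9% / 14.1% | 0.524 | 2.35% / 2.7% |

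With no exits the error is 2.0%. Moving a quarter of the exits before week 6 turns overstatement (q above 0.50) into understatement in two of the three rows. If Worst Knee Pain is not collected between visits, the only score to carry before Week 26 is the baseline 4 to 8, and LOCF cannot create a response.

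**3. Exits and replacements kept in the denominator.** Suppose k early exits are non-responders and the others respond at 65% (k assumed).

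| k | Not replaced: P(Bin(150 − k, 0.65) ≥ 88) | Replaced and kept: n, cutoff | P(Bin(150, 0.65) ≥ cutoff) |
|---|---|---|---|
| 3 | 91.7% | 153, 89 | 93.7% |
| 8 | 80% | 158, 92 | 84.8% |
| 15 | 52% | 165, 96 | 63.7% |

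If 65% is instead the rate over all 150 subjects with exits already scored, power is 95.5%.

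**The case against.** **LOCF may not inflate anything.** A reader might infer from the right-hand rows after week 6 that LOCF pushes the false-positive rate well above 2.5%. The documents do not support that as a general statement. It needs nobody to leave in the first six weeks, every exit to be for a reason other than the knee or lack of efficacy, and the score to be collected at the interim contacts, on which the protocol contradicts itself. The 20% exit rate borrows the synopsis dropout figure, which is not tied to the first 6 months. Under *within the 6 months*, or the any-time definition behind the 70% benchmark, crediting an early low score would not overstate response. All of this stands. What remains is that LOCF can award a status that the explicit definition says must be observed throughout.

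**The study is not shown to be underpowered.** Section 13 defines the responder probability for a subject, which reads as an all-subject rate. On that reading 95.5% holds at n=150, and 92% at n=120 is conservative. This stands.

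**Replaced failures are probably kept.** One might infer that replacement removes failures from the analysis. The missing-data rule points the other way, because it scores discontinuations rather than dropping them. But it concerns leaving the study and section 11.3 concerns leaving treatment, so one clarifying sentence is still needed.

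**The source of the cutoff of 87 is not stated.** A plain Wald interval would pass 87/150 (lower limit 0.5010), but that this produced the table is an inference.

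**Conclusion.** The table error is definite and needs no assumption. Under the stated rule the n=150 entries at 0.60 and 0.65 should read 66% and 95.5%. The objection to 87 is that it fails the rule as written. Its 3.0% error is secondary, since the stated rule itself has 2.7% at n=120. The conclusion of good power at 65% survives if 65% is the all-subject rate. If 65% describes only the other subjects, power depends on the number of non-responder exits, which the documents do not give.

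The conflict between LOCF and the *throughout* definition is real. The sign and size of its net effect are not established: 0.7% to 14.1% against 2.0%, depending on assumed exit timing, retention and exit share, and no created responses at all if the score is not collected between visits. The case for change is that the rule is incompatible with the definition, not that the error is known to be inflated.

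The status of replaced subjects is a clarification only.

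**What to change.** 1. **Power table.** Replace 72% and 97% with 66% and 95.5%. Note beside it that the n=120 column removes exits while the missing-data rule keeps them, and add power over a range of non-responder exits.
2. **Definitions first.** Reconcile *throughout* with *within the 6 months*, and section 9 with the synopsis, sections 3.1 and 7.4.1 and Appendix 1 on whether Worst Knee Pain is collected at the interim contacts.
3. **If *throughout* stands.** Classify subjects who leave the study before Week 26 as non-responders in the primary analysis. Keep LOCF as a sensitivity analysis and add multiple imputation for exits unrelated to the knee, such as pregnancy.
4. **Analysis set.** Define the primary set as all subjects given the baseline injection, and state in section 11.3 that replaced subjects stay in it. Let the cutoff follow the actual n.

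The drafting cost is a few sentences and one recomputed table. The statistical cost is a lower reported rate and some loss of power, because exits unrelated to the knee also count as failures. Non-responder scoring is therefore partly a trade-off. If many early exits are expected, recheck the sample size.
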